**9.4 If this study has undergone scientific or scholarly review, please indicate which entity performed the review:**

- Cancer Center Protocol Review Committee (PRC) (Full approval is required prior to final CHR approval for cancer-related protocols.)
- CTSI Clinical Research Center (CRC) advisory committee
- Departmental scientific review
- Other:

Specify **Other**:

---

## 10.0 Background

**10.1 Background:**

Noxious stimuli will induce a stress response in humans that activates the autonomic nervous system. This response can be observed in various ways such as peripheral vasoconstriction, increase in circulating catecholamine levels, increase in heart rate and blood pressure, etc. Numerous previous studies have used photoplethysmography (measures change in volume) to record these responses. Photoplethysmography is part of a commonly used noninvasive clinical monitoring system called pulse oximetry.

Heat, cold, and electrical current have been used as noxious stimuli in awake subjects. In surgical patients, tetanic stimulus has been established as a noninvasive, standardized noxious stimulus, that has been compared in intensity to the stimulus of a skin incision. Tetanic stimuli are routinely used during general anesthesia to monitor neuromuscular function.

A photoplethysmogram has two components, commonly referred to as AC and DC. The AC component is due to pulsatile changes in tissue volume (mainly arterial pulsation). The DC component is due to transmission of light by nonpulsatile tissues, including venous blood and nonpulsatile portions of arterial blood. Noxious stimuli-induced stress responses mediate peripheral vasoconstriction and will decrease the AC and increase the DC component of the photoplethysmogram. It is not known if the location of the tetanic stimulus has an effect on this stress response.

The aim of this study is to investigate the effect of a known noxious stimulus (tetanic stimulus), applied to three different sites, on both the AC and DC components of the photoplethysmogram in order to determine which component is best in detecting perioperative stress responses and if the location of the stimulus has an effect on the stress response.

**10.2 Preliminary studies:**

Numerous studies have 1) established the tetanic stimulus as a standardized noxious stimulus during general anesthesia, and 2) documented the resulting stress responses using various combinations of anesthetics. However, no data exist on the effect of the location of the tetanic stimulus on the stress response.

During several of my previous intraoperative studies using photoplethysmography, I have observed both the tetanic stimulus and surgical stimulus to have an effect on both the AC and DC components of the photoplethysmogram. Unfortunately, those previous studies were not designed specifically to study and record the effect of the location of the tetanic stimulus on the photoplethysmogram.

**THIS STUDY IS IDENTICAL TO A RECENTLY COMPLETED STUDY (15-17499) WITH THE DIFFERENCE THAT TETANIC STIMULUS WILL BE ADMINISTERED TO ADDITIONAL SITES (ULNAR NERVE, MID AXILLARY LINE OF THORAX AND OVER TIBIA)**

## 11.0 Sample Size and Eligibility

### 11.1 Number of subjects that will be enrolled at UCSF and affiliated institutions:

20

### 11.2 Total number of subjects that will be enrolled at all sites (Help Text updated 9/13):

20

### 11.3 Estimated number of people that you will need to consent and screen here (but not necessarily enroll) to get the needed subjects:

30

**11.4 Explain how and why the number of subjects was chosen (Help Text updated 9/13):**

Based on the previously completed trial, 12 subjects will be needed. I'm requesting to study up to 20 patients in case there will be patients with poor technical data quality.

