## 8.0 Study Design

**8.1 \* Study design (Help Text updated 9/13):**

This is a single center, clinical research study that plans to enroll 20 surgical patients undergoing general anesthesia.

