## 9.0 Scientific Considerations

**9.1 Hypothesis (Help Text updated 9/13):**

This study has a hypothesis:

Yes  No

If yes, state the hypothesis or hypotheses:

During general anesthesia a tetanic stimulus-induced noxious stimulus will elicit a brief peripheral vasoconstrictive response which can be measured as a decrease in the AC component of a photoplethysmogram, and an increase in the DC component of the photoplethysmogram. The hypothesis of this study is that the location where the tetanic stimulus is applied has no effect on the peripheral vasoconstrictive response.

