**9.3 Statistical analysis:**

Maximum changes in the AC and DC components of the photoplethysmogram will be determined during a 60 second period after a tetanic stimulus. Maximum changes in the AC and DC components will be compared to their respective baseline values using paired students t-test.  $p < 0.05$  will signify statistical significance. The maximum changes in the AC and DC components between the three different sites will be compared using ANOVA.

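### The stated need for 12 subjects has no documented basis for the no-effect-of-location hypothesis, and a non-significant ANOVA at 12 to 20 patients could not confirm it

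*Combined protocol and SAP*

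**What the plan says.** Section 11.4 gives the whole sample-size rationale: "Based on the previously completed trial, 12 subjects will be needed". It then adds "I'm requesting to study up to 20 patients in case there will be patients with poor technical data quality". It does not name the earlier trial.

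Section 8.1 says the study "plans to enroll 20 surgical patients undergoing general anesthesia". Sections 11.1 and 11.2 also give 20, and 11.3 gives 30 to consent and screen.

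Section 9.1 states the study hypothesis as "the location where the tetanic stimulus is applied has no effect on the peripheral vasoconstrictive response". Section 9.3 has two analyses: a paired t-test of the maximum AC and DC change against baseline, and an ANOVA of those changes across the three sites. The criterion is p < 0.05. No equivalence margin, confidence interval or power figure appears anywhere.

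Section 10.2 says that "no data exist on the effect of the location of the tetanic stimulus on the stress response". It adds that the investigator's previous studies were not designed to record a location effect. It calls this study identical to the recently completed study 15-17499 apart from the added stimulation sites.

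**The concern.** The title, the aim in 9.2 and the hypothesis in 9.1 all concern stimulus location. The only stated source for the sample size is a trial that, on the account in 10.2, cannot have supplied data on the effect of location. The study's main comparison therefore has no documented size calculation.

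The direction of the hypothesis makes this more serious. When the prediction is a difference, a study that is too small tends to fail. When the prediction is no effect and the only test is a conventional ANOVA, a study that is too small tends to appear to succeed: the fewer the patients, the likelier a non-significant result, and the likelier it is to be reported as confirming 9.1. What is at stake is whether the trial's main conclusion would rest on evidence or on lack of precision.

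**Working it through.** **Inputs from the documents.** 12 needed and up to 20 enrolled (11.4); 20 enrolled (8.1, 11.1, 11.2); p < 0.05 (9.3, taken as two-sided); three sites, each stimulated twice in every patient in random order (13.1). Power, effect size, SD and margin are not given.

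**The plan's own figure.** The 12 cannot be reproduced, because none of the quantities needed to derive it is stated. The step from 12 to 20 can be: 12/(1 − 0.40) = 20, an implied loss of 8/20 = 40%. The documents do not state or justify that rate.

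**Assumptions for what follows.** The unit is the SD of the within-patient difference between two sites, taking one value per patient per site. The documents give no physical SD, so all results are illustrative. Section 9.3 does not say that the ANOVA is repeated-measures; the calculation assumes that it is.

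**1. Precision of one site difference.** 95% CI half-width = t(0.975, n−1)/√n.
- n = 12: 2.201/3.464 = 0.64
- n = 20: 2.093/4.472 = 0.47

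**2. What the ANOVA can detect.** Assume sphericity, with the third site midway between the extremes. A difference of 1 SD unit between sites implies a within-site error variance of 0.5. The noncentrality is then λ = n × 2(δ/2)²/0.5 = nδ², with 2 and 2(n−1) degrees of freedom. For 80% power:
- n = 12: δ = 0.96 (λ = 12 × 0.961² = 11.1)
- n = 20: δ = 0.72 (λ = 20 × 0.722² = 10.4)

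For a true extreme-site difference of 0.5 SD, λ is 12 × 0.25 = 3 and 20 × 0.25 = 5. Power is 28.5% and 47%, so the ANOVA would more often than not miss such a difference.

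**3. Chance of showing similarity when the sites are truly identical.** This is the probability that the 90% CI for a paired difference lies within ± margin (two one-sided tests at 0.05). The one-pair column is exact. The three-pair column is simulated with independent site residuals. The margins are assumptions.

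| Margin (SD) | One pair, n=12 / n=20 | All three pairs, n=12 / n=20 | n for 80%, one pair |
|---|---|---|---|
| 0.3 | 0.2% / 0.8% | not run | 97 |
| 0.5 | 11% / 39% | 1% / 12% | 36 |
| 0.75 | 57% / 89% | 27% / 74% | 17 |
| 1.0 | 89% / 99% | 75% / 98% | 11 |

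Put the other way, 80% power for one pair needs a margin of about 0.90 SD at n = 12 and 0.68 SD at n = 20.

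The low figure at 0.5 SD is easily explained: with the sample SD equal to 1, the 90% CI half-width at n = 12 is 1.796/3.464 = 0.52, already wider than the margin.

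**The case against.** The strongest reply is that 11.4 does not say how 12 was obtained, and the earlier trial is not available here. It may have supplied a response size or variability that was combined with an assumed site difference. Even the identification with study 15-17499 is an inference from 10.2, although a strong one. This stands as a limit: what can be shown is that 12 is undocumented for the location comparison, not that it was derived for something else.

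The result also depends on the margin. At 1.0 SD, 12 patients are enough for one pair. That is true, and it is why a range is shown. But the plan states no margin, so it cannot claim the benefit of a wide one.

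A reader might go further in three ways that the documents do not support.

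- **That the plan contradicts itself on 12 versus 20.** It does not. Section 11.4 presents 12 as needed and up to 20 as cover for unusable recordings, and 8.1, 11.1 and 11.2 all say 20. What remains is smaller: the 40% allowance is unexplained, poor data quality has no criterion, and no rule says whether enrolment stops at 12 usable patients.
- **That this gap inflates the type I error through repeated testing.** No interim look is described, 11.4 ties the extra patients to technical quality, and 13.1 has the data analysed offline. In any case, inflated false rejection works against a no-effect hypothesis, so it would not measure the harm described here.
- **That 12 is adequate for the before/after t-test.** A paired test with 12 has 80% power for a standardised change of 0.89, so 12 is plausible for a large response. No figure in the documents shows that the response is that large.

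**Conclusion.** The point holds in this form: the documents give no basis for 12 as a size for the location comparison, and the analysis in 9.3 cannot turn a non-significant result into support for 9.1. At both ends of the possible analysed number, 12 to 20, the interval for a site difference would extend about 0.64 to 0.47 SD either side of the estimate. The ANOVA would have 80% power only for extreme-site differences of 0.96 to 0.72 SD.

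These sizes rest on SD units, a repeated-measures analysis with sphericity, and margins chosen for illustration. Whether 0.5 or 1.0 SD matters physiologically cannot be judged from the documents. The conclusion about inference does not depend on those choices: with no margin and no interval, p>0.05 does not show that location has no effect.

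**What to change.** - **Section 11.4.** State that 12 was not derived for the between-site comparison (or, if it was, give the assumed difference, SD and power). Give the expected precision of the site contrast at 12 and at 20, labelled as being in SD units unless the earlier trial supplies a usable SD.
- **Section 9.3.** Report the within-patient site differences in AC and DC with confidence intervals. State that absence of a location effect will not be concluded from p>0.05, and that similarity will be claimed only if the interval lies within a margin stated in advance.
- **Analysed set.** Analyse all technically usable patients among the 20 already planned, with a written criterion for usability applied without regard to the site results.

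The cost is rewording and a little analysis, with no added patients or procedures. The downside is a less favourable stated precision and a weaker permitted conclusion: an estimate with its interval, unless a margin is set beforehand and met.

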**11.5 \* Eligible age range(s):**

- 0-6 years
- 7-12 years
- 13-17 years
- 18+ years

**11.6 Inclusion criteria:**

- 1) 18 years old or older
- 2) Willing to participate (signed informed consent)
- 3) English speaking (for consent reasons)
- 4) Surgery under general anesthesia

**11.7 Exclusion criteria:**

- 1) Unable to consent
- 2) Non english speaking
- 4) Under 18 years old

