## 13.0 Procedures

**13.1 \* Procedures/Methods (Help Text updated 9/13)**

**For clinical research list all study procedures, test and treatments required for this study, including when and how often they will be performed. If there are no clinical procedures, describe the Methods:**

In addition to the clinically used pulse oximeter probe, two additional, noninvasive pulse oximeter probes (Masimo, Irvine CA, identical to the one used clinically) will be applied to both index fingers after induction of anesthesia. The probes are noninvasive and pose no known additional risk. Data from these probes will be collected using a laptop computer and ADC software, which is designed to collect photoplethysmography data from Masimo pulse oximeters. Data will be collected while patients are anesthetized. Data will be analyzed offline.

In addition to the pulse oximeter data, other available hemodynamic data will be collected electronically from GE hemodynamic monitors using another laptop computer and S/5 Collect software, which is commercially available for this purpose.

Tetanic stimulus: The study will use the same neuromuscular function monitor as is used clinically. Tetanic stimuli will be applied to the ulnar nerve, thorax at mid axillary line and over tibia. A 5 second, 100 Hz, 60 mA, stimulus will be used (similar to the one used clinically). Tetanus will be applied twice at each location (random order, minimum of 2 minutes apart).

Other than electronic data collection and addition of the two noninvasive pulse oximeter probes and periodic tetanic stimuli, this study will have no influence on surgery, anesthesia, or hemodynamic

monitoring, all of which are left to the discretion of the surgeon and anesthesiologist in charge of the patient.

In summary, the following data will be recorded:

1. Demographic data from APEX
2. Pulse oximeter data will be collected electronically using a laptop computer
3. Anesthetic agents will be recorded from APEX
4. Timing and location of the tetanic stimuli will be marked on the laptop computer.
5. All available electronic monitoring data (blood pressure, heart rate etc.) will be recorded electronically from the operating room hemodynamic monitors using a laptop computer.

If you have a procedure table, attach it to the submission with your other study documents.

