## 14.0 Risks and Benefits

### 14.1 \* Risks and discomforts:

Risks: Pulse oximeter probes are noninvasive and have no known associated risks. Electronic data collection has no known associated risks. Tetanic stimulus has no known associated risks, and will not cause discomfort as the study will be done during general anesthesia.

Benefits: None

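### Eligibility does not address patients with implanted electrical devices, although every patient is to receive research-only stimuli on the thorax and the risk sections do not consider that site

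*Combined protocol and SAP*

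**What the plan says.** **Who may enter.** Section 11.6 asks for adult age, signed consent, English, and "4) Surgery under general anesthesia". Section 11.7 lists "1) Unable to consent", "2) Non english speaking" and "4) Under 18 years old". The numbering runs 1, 2, 4; no item 3 is printed.

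**What is done.** Section 13.1 states: "Tetanic stimuli will be applied to the ulnar nerve, thorax at mid axillary line and over tibia". It continues: "A 5 second, 100 Hz, 60 mA, stimulus will be used (similar to the one used clinically". Each site is stimulated twice. Section 10.2 describes the study as the same as a completed one except that "TETANIC STIMULUS WILL BE ADMINISTERED TO ADDITIONAL SITES (ULNAR NERVE, MID AXILLARY LINE OF THORAX AND OVER TIBIA".

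**What is said about risk.** Section 14.1 states: "Tetanic stimulus has no known associated risks, and will not cause discomfort as the study will be done during general anesthesia". The same section says there are no benefits. Sections 14.2 (steps to minimize risk) and 14.5 (why the risks are reasonable) each answer only that none are known. None of the three distinguishes one stimulation site from another.

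**What supports the stimulus.** Section 10.1 describes tetanic stimulation as routine during general anesthesia for monitoring neuromuscular function.

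**The concern.** Read together, these sections let a patient with an implanted pacemaker, defibrillator or other electrical stimulator into the study, and such a patient would be stimulated on the thorax like everyone else. The stimulus is given for research and the plan claims no benefit to the patient, so the eligibility rules and the risk section have to carry the safety case. Neither mentions implanted devices, and the risk section does not discuss the thorax.

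That a device sensing electrical activity in the chest might misread current applied to the chest wall is a general electrical-safety consideration. It is the reason to ask the question. It does not come from the protocol, and the protocol gives no probability for it.

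**Working it through.** The plan states no figure on this point, so the check is a reading of the sections against one another plus a count of the exposure.

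**Step 1: does any visible criterion keep such a patient out?**

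| Exclusion shown in 11.7 | Matching inclusion in 11.6 |
|---|---|
| Item 1, inability to consent | Item 2, signed consent |
| Item 2, language | Item 3, English |
| Item 3 | not printed |
| Item 4, age | Item 1, age |

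Each visible exclusion mirrors an inclusion criterion, so the printed list removes nobody that 11.6 has not already removed. The one remaining inclusion, surgery under general anesthesia, does not restrict by medical history.

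**Step 2: does any other section keep such a patient out?**

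- 17.2: the investigator picks likely suitable patients from the operating room schedule; suitability is not defined.
- 17.3: patients are approached on arrival in the preoperative area; no device check is described.
- 18.5: schedules are screened against the inclusion criteria, which contain no device item.
- 13.1: the procedure has no exception for any type of patient.
- 13.8: an anesthesiologist is present. That bears on responding to an event and does not decide who is stimulated.

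**Step 3: what is the exposure?** Inputs from 13.1 are 3 sites, 2 stimuli per site, 5 s each, 100 Hz, 60 mA. The enrollment of 20 is from 11.1.

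- Stimuli per patient: 3 × 2 = 6, of which 2 are thoracic.
- Thoracic stimulation per patient: 2 × 5 s = 10 s.
- Thoracic pulses per patient, at one pulse per cycle: 10 s × 100 per s = 1,000.
- Thoracic stimuli in the whole study: at most 20 × 2 = 40. With the 12 patients that 11.4 says are needed, 12 × 2 = 24.

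These counts describe what any enrolled patient receives. They do not measure harm.

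**Step 4: does the stated rationale reach the thorax?** Section 10.1 makes tetanic stimulation routine for one purpose, neuromuscular monitoring, and names no site for that use. The comparison with clinical practice in 13.1 follows the duration, frequency and current of the stimulus; it does not say that the chest wall is a clinical site. Section 10.2 includes the thorax among the additional sites. No section therefore says that routine experience covers the thoracic stimulus.

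**The case against.** The strongest objection is that the hazard is not in the documents. Nothing in them says that a tetanic stimulus disturbs an implanted device. This stands, and it limits the point to a gap: a group of patients the plan admits and never considers. The gap itself can be read directly from the sections and does not depend on how likely interference is.

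A second objection is that the exclusion list may be incomplete. Item 3 could have been deleted by the author or lost when the text was read. This also stands. No other section suggests that it concerned devices, but only the sponsor can confirm it. The consent pages are not in the copy reviewed, so what patients are told or asked there is unknown.

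A third is that a faculty anesthesiologist selects the patients and an anesthesiologist is present. These are real general safeguards, and in practice such a patient might well not be approached. They are not a rule, however, and someone following the visible criteria exactly would have no reason to decline the patient.

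Several stronger readings are tempting and are not supported:

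- *That a minimal-risk classification is wrong.* The selection in 5.2 cannot be read, and the minimal-risk wording in 18.2 concerns privacy in record screening.
- *That two of the three sites are new to clinical use.* Section 10.2 puts all three, including the ulnar nerve, under additional sites; no section says which are routine or which the completed study used.
- *That enrolling a device patient is likely.* The documents give no prevalence. Any figure would rest on an assumed one, and would be a chance of enrollment, not of harm.
- *That a device response would bias the comparison between sites.* Nothing in the documents supports or sizes this.

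**Conclusion.** The concern holds as a gap between eligibility, procedure and risk assessment. As printed, the criteria would allow a patient with an implanted electrical device to receive two thoracic trains, 10 s in all, for research only. The risk answers in 14.1, 14.2 and 14.5 make a blanket statement without considering that site, and the rationale in 10.1 and 13.1 does not say that the chest wall is a routine one.

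The conclusion assumes that the missing exclusion item 3 does not cover implanted devices; if it does, the eligibility part falls away and only the risk wording remains. It also rests on general electrical-safety reasoning for why the omission matters. No probability of interference can be derived from the documents, and none is claimed. The change is worth making because it affects who is stimulated and costs very little.

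**What to change.** 1. Confirm what exclusion item 3 in 11.7 was, and restore it or correct the numbering.
2. If it does not cover implanted devices, reconcile 11.7 with the thoracic stimulus in 13.1 by adding an eligibility line that addresses patients with a pacemaker, defibrillator or other implanted electrical stimulator, for example by not enrolling them.
3. In 14.1, 14.2 and 14.5, replace the blanket answer with one specific to the thoracic site. It should say what is known about stimulation there, whether patients with implanted devices were considered, and what is done about them.

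The cost is a few lines of text and a device check before enrollment. The downside is that a few otherwise eligible patients would not be approached. Section 11.3 already allows for 30 people consented and screened to enroll 20, a margin of 30 − 20 = 10, and 11.4 puts the number needed at 12.
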